1. SCHEMA

CYTARABINE PLUS CONTINUOUS INFUSION DAUNORUBICIN, WITH CARDIAC
MRI MONITORING, INDUCTION THERAPY FOR ADULTS WITH ACUTE MYELOID
LEUKEMIA; A FEASIBILITY STUDY

Wake Forest Baptist Comprehensive Cancer Center (WFBCCC) CCCWFU 22616

1.0 Introduction and Background

It is estimated that 19,950 people will be diagnosed with acute myeloid leukemia (AML) and 10,430 will die from it in the United States in 2016.¹ Standard induction therapy for patients with good performance status consists of a 7+3 regimen of cytarabine 100-200 mg/m² continuous infusion x 7 days with an anthracycline, i.e. daunorubicin 60-90 mg/m² (45-90 mg/m² for patients \geq 60 years or idarubicin 12 mg/m²) x 3 days.² While advances in treatment have resulted in substantially improved complete remission (CR) rates, with 60% to 70% of adults expected to attain CR status following appropriate induction therapy, only slightly more than 25% (about 45% of those who attain CR) can be expected to survive 3 or more years.

1.1 Chemotherapy-induced cardiotoxicity

Along with myelosuppression, cardiac effects are the key dose-limiting toxicities of daunorubicin and other drugs in the anthracyclines class. Treatment with daunorubicin can result in arrhythmias and cardiomyopathy, with a maximum total (lifetime) dose of 500-600 mg/m² recommended because of cumulative cardiotoxicity. Currently there is no reliable method of predicting patients at increased risk for developing cardiotoxicity. Transthoracic echocardiography is used most widely to measure cardiac function and volume because of its availability, anatomic and prognostic validation, and lack of ionizing radiation.³⁻⁵ Furthermore, when cardiac chambers contract in a uniform and symmetric pattern, a close correlation is found between echocardiographic and angiographic volume measurements.⁶ Limitations of echocardiography include difficulty in assessing the apex and right ventricle. In addition, assumptions regarding the geometry of the LV (as a prolate ellipsoid) are used to estimate ventricular volumes and mass. MRI acquires tomographic 2D or 3D images of the entire heart. Volumetric assessment of the LV is independent of geometric assumptions, noninvasive, and free of exposure to contrast agents or ionizing radiation. MRI is considered superior to other imaging techniques because of its capability for high-resolution measurements of anatomy and function of the LV.⁷ Cardiac MRI was successfully implemented in the Multi-Ethnic Study of Atherosclerosis (MESA), sponsored by the National Heart, Lung, and Blood Institute of the National Institutes of Health.⁸

1.2 Daunorubicin administration

Previous studies in patients with advanced breast and ovarian cancer and metastatic soft tissue sarcoma have examined cardiotoxicity outcomes with bolus versus continuous infusion administration of anthracyclines and found a decreased risk with continuous infusion.⁹⁻¹¹ A Southwest Oncology Group study in AML patients included infusional daunorubicin and cytarabine with and without cyclosporin and concluded that infusional daunorubicin did not significantly alter the toxicity profile or efficacy of the standard 7+3 regimen, although, this was not the main objective of the study.¹²

There is limited but sufficient evidence to suggest that daunorubicin administered as a continuous infusion rather than bolus in the standard 7+3 regimen would provide a reduced risk of cardiotoxic effects with at least similar response rates. As such, this study aims to assess the safety and feasibility of administering daunorubicin as a continuous infusion in patients undergoing induction therapy for newly diagnosed AML.

**CYTARABINE PLUS CONTINUOUS INFUSION DAUNORUBICIN, WITH CARDIAC
MRI MONITORING, INDUCTION THERAPY FOR ADULTS WITH ACUTE MYELOID
LEUKEMIA; A FEASIBILITY STUDY**

Wake Forest Baptist Comprehensive Cancer Center (WFBCCC) CCCWFU 22616

We will assess clinical outcomes under the proposed regimen, as well as examine the use of cardiac MRI in identifying cardiac toxicity.

2.0 Objectives

2.1 Primary Objectives

- 2.1.1 To assess the safety (at 3 months) and feasibility of administering daunorubicin as continuous infusion under the proposed treatment regimen.

2.2 Secondary Objectives

- 2.2.1 To assess the safety (at 6 months) of administering daunorubicin as continuous infusion under the proposed treatment regimen.
- 2.2.2 To assess treatment outcomes (including CR and CRi) in patients with AML under the proposed treatment regimen.
- 2.2.3 To compare the concordance between MRI and ECHO in identifying cardiac toxicity, i.e. a reduction in LVEF of $\geq 10\%$ and $EF \leq 50\%$ compared to baseline LVEF.

3.0 Patient Selection

3.1 Inclusion Criteria

- 3.1.1 Patients must have morphologically confirmed newly diagnosed acute myelogenous leukemia (AML) with blood or bone marrow disease. Patients with only extramedullary disease in the absence of bone marrow or blood involvement are eligible. Note: This protocol uses WHO diagnostic criteria for AML. Patients with acute promyelocytic leukemia (APL, FAB, M3) or blastic transformation of chronic myelogenous leukemia (CML) are not eligible.
- 3.1.2 ≥ 18 years of age.
- 3.1.3 ECOG performance status 0-3.
- 3.1.4 Patients with ECHO EF $\geq 45\%$ within 28 days prior to registration.
- 3.1.5 Because of the teratogenic potential of the drugs used in this study, women of child-bearing potential and men must agree to use adequate contraception (hormonal or barrier method of birth control; abstinence) prior to study entry and for the duration of study participation. Should a woman become pregnant or suspect she is pregnant while participating in this study, she should inform her treating physician immediately.
- 3.1.6 Ability to understand and the willingness to sign an IRB-approved informed consent document.

CYTARABINE PLUS CONTINUOUS INFUSION DAUNORUBICIN, WITH CARDIAC MRI MONITORING, INDUCTION THERAPY FOR ADULTS WITH ACUTE MYELOID LEUKEMIA; A FEASIBILITY STUDY

Wake Forest Baptist Comprehensive Cancer Center (WFBCCC) CCCWFU 22616

3.2 Exclusion Criteria

- 3.2.1 Patients who have received prior induction chemotherapy for AML or MDS. Temporary prior measures such as apheresis or hydroxyurea are allowed. Patients who have received a limited and short-term exposure of ATRA (all trans retinoic acid) while AML-M3 (Acute Promyelocytic Leukemia) was being ruled out, and which has been discontinued, will be eligible.
- 3.2.2 Patients receiving any other investigational agents.
- 3.2.3 Patients with prolonged QTc interval (> 500 msec) determined by EKG within 28 days prior to registration.
- 3.2.4 Patients not suitable for cardiac MRI. Contraindications include:
 - Intracranial metal, pacemakers, defibrillators, functioning neurostimulator devices, or other implanted electronic devices
 - Ferromagnetic cerebral aneurysm clips, or other intraorbital/intracranial metal
 - Allergy to Gadolinium or other severe drug allergies
 - Claustrophobia
 - Congestive heart failure (NYHA class III or IV)
 - Significant valvular disease, or significant pulmonary disease requiring supplemental oxygen therapy
- 3.2.5 History of allergic reactions attributed to compounds of similar chemical or biologic composition to daunorubicin or cytarabine.
- 3.2.6 Patients with documented CNS involvement.
- 3.2.7 Patients who are known to be HIV+ may be eligible providing they meet all of the following additional criteria within 28 days prior to registration:
 - CD4 cells \geq 500/mm³
 - Viral load of < 50 copies HIV mRNA/mm³ if on cART or < 25,000 copies HIV mRNA if not on cART
 - No zidovudine or stavudine as part of cART

Patients who are HIV+ and do not meet all of these criteria are not eligible for this study.
- 3.2.8 Patients with other uncontrolled intercurrent illness or psychiatric illness/social situations that would limit compliance with study requirements.
- 3.2.9 Pregnant women are excluded from this study because of the potential for teratogenic or abortifacient effects with drugs used in this study. Because there is an unknown but potential risk for adverse events in nursing infants

CYTARABINE PLUS CONTINUOUS INFUSION DAUNORUBICIN, WITH CARDIAC
MRI MONITORING, INDUCTION THERAPY FOR ADULTS WITH ACUTE MYELOID
LEUKEMIA; A FEASIBILITY STUDY

Wake Forest Baptist Comprehensive Cancer Center (WFBCCC) CCCWFU 22616

secondary to treatment of the mother with the drugs used in this study, breastfeeding should be discontinued prior to beginning treatment.

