6.1 Treatment Administration

Treatment will be administered on an inpatient basis. Reported adverse events and potential risks are described in Section 9. No investigational or commercial agents or therapies other than those described below may be administered with the intent to treat the patient's malignancy.

Agent	Dose	Route	Schedule	Cycle Length
Induction				
Cytarabine	100 mg/m ² /day	IV infusion	Days 1-7	14 days
Daunorubicin	60 mg/m ² /day	IV infusion	Days 1-3	
Re-induction (if needed)				
Cytarabine	100 mg/m ² /day	IV infusion	Days 1-5	14 days
Daunorubicin	60 mg/m ² /day	IV infusion	Days 1-2	
Consolidation (up to 3 cycles, or up to 4 cycles for CBF AML)				
Cytarabine	<60 yrs: 3,000 mg/m ² /day ≥ 60 yrs: 1,500 mg/m ² /day	IV infusion over 3 hours, every 12 hours	Days 1,3,5	≥ 28 days

Induction: This study regimen will follow the standard 7+3 regimen of cytarabine and daunorubicin, with the modification of daunorubicin administered as continuous infusion rather than bolus. Baseline troponin I, full 3D ECHO, and MRI without contrast will be performed prior to treatment.

For troponin determination, the study will use either the TnI-Ultra™ assay, Siemens, Munich Germany or the Beckman Coulter Access 2 AccuTnI+3 assay for detection of troponin I. While the assays are comparable, every effort will be made to test all samples on the current Institutional standard troponin I testing platform (TnI-Ultra assay, Siemens). If the TnI-Ultra assay becomes unavailable either because of changing Institutional standards or product availability the Beckman Coulter Access 2 AccuTnI+3 assay will be utilized. The brand of assay and results will be recorded for each test on the Cardiac Function Worksheet.

Patients will have a bone marrow aspirate and biopsy on day 14 (± 2 days).

Re-induction: A second induction course may be given if the day 14 bone marrow aspirate and biopsy shows bone marrow cellularity as $\geq 10\%$ and $> 5\%$ leukemic blasts. Those requiring re-induction will undergo a limited ECHO with strain measures prior to treatment. This abbreviated cycle will consist of cytarabine on days 1-5 and daunorubicin on days 1 and 2, with a troponin I measure on day 3 and a bone marrow biopsy on day 14 (± 2 days). Patients not achieving a remission after 2 induction attempts will be removed from study.

CYTARABINE PLUS CONTINUOUS INFUSION DAUNORUBICIN, WITH CARDIAC
MRI MONITORING, INDUCTION THERAPY FOR ADULTS WITH ACUTE MYELOID

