LEUKEMIA; A FEASIBILITY STUDY

Wake Forest Baptist Comprehensive Cancer Center (WFBCCC) CCCWFU 22616

Patients without bone marrow involvement at diagnosis will receive a second induction course if they have not cleared their soft tissue disease by day 14 (± 2 days).

If cellularity is $<10\%$ on day 14, a repeat bone marrow biopsy should be obtained as clinically indicated. Treatment response will be evaluated once ANC $>1,000 / \mu\text{L}$ and platelets $\geq 100,000 / \mu\text{L}$, but no later than day 42. If peripheral blood counts are inadequate (ANC $<1,000 / \mu\text{L}$, platelets $<100,000 / \mu\text{L}$) at the time of this bone marrow aspirate and biopsy, a repeat bone marrow aspirate and biopsy must be obtained to document complete remission at the time of peripheral blood count recovery (ANC $\geq 1,000 / \mu\text{L}$, platelets $\geq 100,000 / \mu\text{L}$) if > 1 week after "day 42" bone marrow study.

Physicians should consider earlier bone marrow exams in patients whose peripheral blood counts are not recovering or recovering sluggishly, as well as in patients whose day 14 bone marrow was suspicious for residual leukemia.

Consolidation: Patients in remission will receive high-dose cytarabine (days 1, 3, and 5) consolidation therapy for up to 3 cycles (except in the case of toxicity or receipt of stem cell transplant). Patients with core-binding factor (CBF) AML may receive 4 cycles of consolidation therapy. Therapy should be started as soon as possible (and within 14 days) after recovery from induction/re-induction therapy.

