7.0 Dose Modifications

Induction: no dose reductions allowed.

Re-induction: Dose reductions may be allowed in the setting of hepatotoxicity as follows:

- For SGPT/SGOT 150-300 U/L **OR** bilirubin 1.5-3.0 mg/dL, reduce daunorubicin dose to 45 mg/m²/day.
- For SGPT/SGOT > 300 U/L **OR** bilirubin > 3.0-5.0 mg/dL, reduce daunorubicin dose to 30 mg/m²/day.

Consolidation: No dose reductions allowed for Cycle 1 except in the instance of renal dysfunction, as follows:

- For creatinine greater than 2 mg/dL or calculated creatinine clearance of < 50 mL/min, decrease cytarabine dose to 1,000 mg/m²/dose.
- For creatinine greater than 3 mg/dL or calculated creatinine clearance of < 30 mL/min, change cytarabine to 400 mg/m²/day IV infusion over 24 hours daily for 5 days.

For consolidation cycles beyond Cycle 1, doses of cytarabine may be reduced by 750 mg/m²/day for the following reasons:

- Grade 3-4 non-hematologic toxicity
- Severe life-threatening infection

If toxicity persists, cytarabine dose may be reduced by an additional 750 mg/m²/day.

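### No eligibility or dose rule counts anthracycline given for an earlier cancer, so a pre-exposed patient with preserved cardiac function could pass the lifetime daunorubicin maximum the protocol cites

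*Combined protocol and SAP*

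**What the plan says.** **The limit.** Section 1.1 refers to a "maximum total (lifetime) dose of 500-600 mg/m² recommended because of cumulative cardiotoxicity". This is background text, and no later section turns it into a rule.

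**The dose.** Section 6.1 gives daunorubicin 60 mg/m²/day for three days at induction. For re-induction, at the same daily dose, "This abbreviated cycle will consist of cytarabine on days 1-5 and daunorubicin on days 1 and 2". Consolidation is cytarabine without an anthracycline. In marrow disease re-induction is optional: "A second induction course may be given if the day 14 bone marrow aspirate and biopsy shows" at least 10% cellularity with more than 5% leukemic blasts. For extramedullary-only disease it is worded as an instruction: "Patients without bone marrow involvement at diagnosis will receive a second induction course if they have not cleared their soft tissue disease" by day 14.

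**Dose changes.** Section 7.0 states "Induction: no dose reductions allowed". For re-induction, "Dose reductions may be allowed in the setting of hepatotoxicity as follows", with daunorubicin lowered to 45 or 30 mg/m²/day.

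**Who may enter.** Section 3.1.1 takes newly diagnosed AML by WHO criteria and rules out two disease types: "Patients with acute promyelocytic leukemia (APL, FAB, M3) or blastic transformation of chronic myelogenous leukemia (CML) are not eligible". Section 3.2.1 rules out "Patients who have received prior induction chemotherapy for AML or MDS". Appendix B repeats both.

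**Cardiac safeguards.** These are ECHO EF of at least 45%, exclusions for NYHA III/IV heart failure, significant valvular disease and QTc above 500 msec, baseline ECHO, MRI and troponin I, troponin during each induction course, and a limited ECHO before re-induction.

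**The concern.** The protocol ties cardiac risk to cumulative dose and cites a ceiling, but its operating rules look only at the present state of the heart. A patient whose AML follows treatment of another cancer with an anthracycline meets the diagnosis criterion and is not caught by 3.2.1. If EF is preserved, nothing written asks how much anthracycline has already been given or adds the study dose to it.

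At stake is patient safety in a trial whose primary objective is the safety of infusional daunorubicin and whose first primary outcome is cardiac toxicity. A lesser consequence is interpretation. With prior exposure unrecorded, a reader of a single-arm 3-month event rate cannot tell whether an event occurred in a patient who arrived already exposed. Section 13.2 stratifies treatment outcomes by age, ECOG, cytogenetic risk and prior hematological disease, but not by prior anthracycline.

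**Working it through.** **Inputs.** The cited maximum is 500-600 mg/m² (1.1). Daunorubicin is 60 mg/m²/day for 3 days, then for 2 days if re-induced (6.1), with re-induction at 45 or 30 mg/m²/day for hepatotoxicity only (7.0). The maximum is a cited figure, so there is no derivation in the plan to reproduce.

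**Formula.** Room for prior exposure = limit − on-study daunorubicin. A prior dose above that room takes the total past the limit. All figures are in mg/m², with prior dose in daunorubicin equivalents.

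| Daunorubicin received on study | On-study total | Room under 500 | Room under 600 |
|---|---|---|---|
| Induction alone | 3 × 60 = 180 | 320 | 420 |
| Plus full-dose re-induction | 180 + 2 × 60 = 300 | 200 | 300 |
| Plus re-induction at 45/day | 180 + 2 × 45 = 270 | 230 | 330 |
| Plus re-induction at 30/day | 180 + 2 × 30 = 240 | 260 | 360 |

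**Anthracycline-naive patient.** The largest on-study total is 300, which is 200 below the lower bound. The regimen alone cannot reach the limit.

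**A pre-exposed patient traced through the text.** Assume a prior dose of 250.

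- Entry: 3.1.1 and 3.2.1 do not exclude the patient, Appendix B has no line on prior exposure, and an EF of 45% or more satisfies 3.1.4.
- Induction: 250 + 180 = 430, below both bounds.
- Re-induction: the limited ECHO is done, but neither 6.1 nor 7.0 names a result that withholds daunorubicin. If the liver tests trigger no reduction, the full dose applies: 250 + 300 = 550, above 500 and below 600.

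With a prior dose of 300, the total after induction is 480. Even the lowest re-induction dose gives 300 + 240 = 540.

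**Where prior dose could have been captured.** The Appendix A registration form and the Appendix E worksheet have no field for it. The schema and the body of the adverse event log are not shown in the available text, so the statement covers reproduced forms only.

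**Sample size.** Section 13.3 is not in question. At n = 32, a paired t-test has 80.0% power at 0.511 SD, and the widest exact interval has half-width 0.181, both as stated.

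**The case against.** The case on the other side has five parts.

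- **No affected patient is shown.** Harm needs a prior dose above 200-420 mg/m², preserved function, and a physician who knows the history and proceeds. At the lower doses it also needs re-induction, which is mandatory only in uncleared extramedullary-only disease. This stands, and it limits the size of the point.
- **The trial adds no dose to usual care.** It follows standard 7+3, and 60 mg/m² is at the bottom of the general 60-90 range in 1.0. That is fair: the design does not create the risk. But a cardiac-safety study that cites a dose ceiling should apply it or explain why not.
- **Safeguards exist.** Medical history is taken, the treating physician signs the checklist, the heart is imaged and troponin measured, and 6.5 lets the investigator stop. These reduce the risk. None totals or caps dose, and the stopping grounds in 6.5 do not include a dose total.
- **The thresholds need inputs the documents lack.** There are no conversion factors, so the figures apply directly only to prior daunorubicin. This stands.
- **The fix moves any excess off study.** The physician can still give an anthracycline off protocol. This is true, and reasonable given the survival figures in 1.0. The rule limits only what the protocol directs.

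A reader might infer that the regimen itself breaches the lifetime maximum, that 500-600 mg/m² is a stopping rule being broken, or that the cardiotoxicity rate will be biased by a known amount. The documents support none of these. Naive patients stay at or below 300 mg/m², the range is background guidance, and there is no input from which to estimate how many patients are pre-exposed or what effect they have.

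**Conclusion.** The gap is real and conditional. The written eligibility and dose rules can take a pre-exposed patient with preserved function past the maximum the protocol cites. This happens at a prior daunorubicin-equivalent dose above 320-420 mg/m² with induction alone, or above 200-300 mg/m² with full-dose re-induction. The ranges come from the two ends of the cited maximum.

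The conclusion assumes that such a patient presents, that the prior dose can be put in daunorubicin equivalents, and that clinical judgment does not intervene first. The number affected may be zero. Any effect on the 3-month rate is likely small and is not quantified here. This is a cheap improvement to patient safety and to reporting; no analysis or power figure is in error.

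**What to change.** 1. **Entry.** Choose one limit from the cited range and agree the conversion factors. Add to 3.2 and Appendix B an exclusion when prior dose plus 180 mg/m² would exceed the limit: prior dose above 320 under a limit of 500, or above 420 under 600.
2. **Re-induction.** Add to 6.1 and 7.0, for both the marrow and the extramedullary-only rules, that protocol daunorubicin is not given at any dose that takes the running total past the limit. Under 500 this bars the full dose above a prior 200 mg/m², 45 mg/m²/day above 230, and every protocol re-induction dose above 260 (under 600: 300, 330 and 360). So among patients admitted with a prior 200-320, those above 260 lose protocol re-induction entirely, not just at full dose. Reduced doses would still apply only for hepatotoxicity.
3. **Follow-up.** Section 6.1 bars anti-leukemia treatment beyond what it describes, although that includes transplant in first remission (6.1.1) and midostaurin for FLT-3 (6.1.2). Patients barred from re-induction may therefore leave protocol treatment for the physician's choice. State in 6.6 that they stay in cardiac follow-up, because the 6-month MRI is now limited to patients still on protocol.
4. **Recording.** Add prior cumulative anthracycline dose to Appendix A or E and list it descriptively beside the 3-month cardiotoxicity rate.

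The cost is one amendment: an exclusion and checklist line, a running-total sentence, a follow-up sentence, a baseline field and a listing, plus agreement on the limit and factors. The downside is possibly a few fewer eligible patients, or a few who leave protocol treatment at re-induction.

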3.3 Inclusion of Women and Minorities

Men and women of all races and ethnicities who meet the above-described eligibility criteria are eligible to participate in this study.

The study consent form will also be provided in Spanish for Spanish-speaking participants. Based on WFBCCC population estimates, we expect approximately 44% of participants to be women. Translating this to our sample size estimate of 40, we plan to enroll at least 18 women. Similarly, we expect approximately 3% of study participants to be Hispanic/Latino (N=1). We plan to enroll at least 11% Black or African American (N=4), 0% American Indian/Alaska Native (N=0), .006% Asian (N=1). Should we not meet or exceed these estimates, the PI will engage the Cancer Center Health Equity Advisory Group to discuss strategies to enhance recruitment in these target populations.

4.0 Registration Procedures

All patients entered on any WFBCCC trial, whether treatment, companion, or cancer control trial, **must** be registered with the WFBCCC Protocol Registrar or entered into ORIS Screening Log within 24 hours of Informed Consent. Patients **must** be registered prior to the initiation of treatment.

You must perform the following steps in order to ensure prompt registration of your patient:

1. Complete the Eligibility Checklist (Appendix B)
2. Complete the Protocol Registration Form (Appendix A)
3. Alert the Cancer Center registrar by phone, *and then* send the signed Informed Consent Form, Eligibility Checklist and Protocol Registration Form to the registrar, either by fax or e-mail.

Contact Information:

Protocol Registrar [contact]

Protocol Registrar [contact]

Protocol Registrar E-MAIL ([contact])

*Protocol Registration is open from 8:30 AM - 4:00 PM, Monday-Friday.

4. Fax/e-mail ALL eligibility source documents with registration. Patients **will not** be registered without all required supporting documents.

Note: If labs were performed at an outside institution, provide a printout of the results. Ensure that the most recent lab values are sent.

To complete the registration process, the Registrar will:

- assign a patient study number
- register the patient on the study

CYTARABINE PLUS CONTINUOUS INFUSION DAUNORUBICIN, WITH CARDIAC
MRI MONITORING, INDUCTION THERAPY FOR ADULTS WITH ACUTE MYELOID
LEUKEMIA; A FEASIBILITY STUDY

Wake Forest Baptist Comprehensive Cancer Center (WFBCCC) CCCWFU 22616

